### 2.7.3 Brainstem Evoked Response Audiometry (BERA)

BERA using a Cadwell 12-channel amplifier at 80 dB was performed when the children reached four months of age. Two independent, trained nurses conducted the assessments. Prior to conducting the assessments on study participants, we evaluated inter-rater reliability between the two assessors using the Intraclass Correlation Coefficient (ICC) in a sample of six children, which resulted an ICC of 0.99. The outcomes derived from this assessment include:

- Absolute latencies for wave I in ms (continuous).
- Absolute latencies for wave III in ms (continuous).
- Absolute latencies for wave V in ms (continuous).
- Interpeak latencies for wave I–III interval in ms (continuous).

- Interpeak latencies for wave III–V interval in ms (continuous).
- Interpeak latencies for wave I–V interval (central conduction time) in ms (continuous).

#### 2.7.4 Eye-tracking assessments

Our eye-tracking assessments adopted a protocol by Prado et al (2020). Eye-tracking-based IOWA and VPC tasks were performed when children reached the age of 6 months in a room with minimal distraction and quiet conditions by a trained psychologist. Children sat on their caregivers' laps, facing the screen. Caregivers were asked to look away from the monitor, close their eyes, or wear a blindfold. A monitor was positioned approximately 60 cm from the child's face. We monitored the caregiver and child using a webcam throughout the procedure. We used Tobii Pro X2–60 as the eye-tracking system to detect child's eye fixations when stimuli were presented on the monitor. The eye-tracking system recorded the coordinates (x, y) of the focal point of the infant's gaze at a rate of 60 Hz. Tobii I-VT Fixation Filter was used to classify fixations.

We will evaluate child attention using the IOWA task based on Ross-Sheehy (2015). This task assesses visual attention based on the precue presented to the children. Each trial of the IOWA task consisted of the following:

1. Central fixation

Before every trial in IOWA task, a central fixation appeared as a bright yellow dynamic smiley face that loomed from small (0° 52' width X 0° 57' height) to large (4° 35' width X 5° 9' height) at a rate of approximately 1.5 Hz, accompanied with classical music. When the infant's gaze was fixed on the central fixation, the eye-tracking assessor pressed a key to advance to the trial.

2. A 100 ms spatial precue depending on the cue type

The trial period in the IOWA task involves several cue types: 3 experimental conditions (*valid*, *invalid*, and *double cues*) and 1 control condition (*no cue*). A black dot serves as a spatial precue preceding a randomly presented target image. The number and location of the presented black dot depend on the types of cue conditions.

3. A 100 ms blank screen

4. A target image displayed for 1000 ms

The target images consisted of 96 colorful everyday objects, some familiar and others unfamiliar to the children, such as fruits, balls, and baskets, on a gray background (RGB: 136, 136, 136).

In the *valid cue* condition, both the cue and target image appeared on the same side, while in the *invalid cue* condition, the target image was presented on the opposite side of the cue. The *double cue* condition involves cues on both sides, with the target image presented at the spatial location of 1 of the 2 cued locations. In the baseline condition, *no cue* is presented, but the target image still appears on either the left or right side of the screen. Each child was exposed to up to 24 trials per cue condition, with half of the target images on the screen's right side. No music or tone was presented during the trials.

The outcomes derived from this task will include:

- IOWA *Mean latency*: Average latency to the target image across all four spatial cues on correct trials (continuous).
- IOWA *Task error*: The degree of interference from the invalid spatial cue that was present in double and invalid cue condition =  $1 - (\text{mean}(\text{Percor\_double}, \text{Percor\_invalid}))$  (continuous).

- IOWA *Cue facilitation*: The degree of facilitation due to the valid cue compared to the no cue condition =  $(\text{Mean\_nocue} - \text{Mean\_valid})/\text{Mean\_nocue}$  (continuous).
- IOWA *Cue interference*: The degree of interference due to the invalid cue compared to the no cue condition =  $(\text{Mean\_invalid} - \text{Mean\_nocue})/\text{Mean\_nocue}$  (continuous).

We will create area of interests (AOIs) around the central fixation, left image, and right image. Based on this AOI, each IOWA trial was classified as correct if the child's first fixation fell on the target image AOI (either left or right) after the onset of this target image. If the trial is correct, we calculated the *mean latency*. We excluded any trials when children looked at the central fixation < 200 ms to ensure that the fixation was in response to the target and not started before the child attended to the target. We also excluded correct trials with mean latency < 100 ms and > 1000 ms. A mean latency of 100 ms is considered too fast to reflect child's response to the target, and a mean latency of 1000 ms may indicate that the child was off-task. Task error will be determined by the proportion of correct in invalid and double cue trials.

We will use the VPC task to assess visual recognition memory. This task has been previously used in diverse contexts. We will compare the proportion of time the child spends looking at a novel face compared to the previously seen face (i.e., novelty preference). VPC consists of four trials for four different pairs of Indonesian faces (i.e., adult male-adult female, adult male-child male, adult female-child female, and child male-child female). Each trial comprises a *familiarization* followed by a *recognition memory* period.

1. Familiarization period: Two culturally familiar faces were presented on the left and right sides of the screen.
2. Recognition memory period: A new pair of faces was presented, consisting of the same face shown in familiarization period (familiar stimulus) on one side and a novel face on the other side. These stimuli were side-reversed after the first 5 seconds.

The outcomes derived from this task will include:

- VPC *Novelty preference score*: Total time looking at the novel stimulus divided by the total time looking at stimulus during the recognition memory period (continuous).
- VPC *Mean familiarization fixation*: Mean fixation across all familiarization trials for which data are available (continuous).

We will create the AOIs for each face that was presented: 1 AOI covered the right side of the screen from the right edge of the central image to the right edge of the screen and from top to bottom, and 1 AOI covered the mirror image on the left side of the screen. We excluded trials with <1 s of looking time during either familiarization or recognition memory periods.

## 2.8. Deviations from Protocol

During COVID-19 pandemic, research activities were strictly adjusted with the COVID-19 prevention measures for both personnel and subjects. Some adjustments for the project field implementation were conducted during the outbreak, including (1) implementing routine COVID-19 screening, providing adequate PPE and education for the fieldworkers about the prevention measures, (2) supplement delivery and anthropometric assessment tools using online motorcycle taxi services with a protocol developed to ensure the safety of supplement bottle transfer from the research personnel to the motorcycle taxi driver, and from the driver to the mothers, including safe distancing and disinfection procedures, (3) educating and providing sanitation supplies to the mothers, (4) mothers might not attend MRI assessment and blood sample collection if not comfortable with visiting non-COVID-18 referral hospital and laboratory. Several implementation protocols—Plan B (social distancing), Plan C (social distancing and remote working), and Plan D

(intensive social distancing and remote working)—were developed and adapted to the evolving pandemic dynamics. These protocols were based on guidance from the Indonesian Ministry of Health, permits from local government and ethics committees, the Data Safety Monitoring Board, and the FDA's Guidance on Conduct of Clinical Trials of Medical Products during the COVID-19 Pandemic.

**Full details of the background to the trial and its design are presented in the protocol.**

### **3. GENERAL STATISTICAL METHODOLOGY**

#### **3.1. Objectives of Analysis Plan**

This analysis plan covers all primary objectives and selected secondary objectives related to fetal brain and infant development assessments.

#### **3.2. Analysis Software**

R version 4.3.2 – primarily used for analyses and results preparation

Stata version 14.1 – primarily used for data cleaning and management

#### **3.3. Data verification**

All data underwent verification, consistency, and range checks prior to analysis. Field supervisors reviewed data entries from enumerators against the source documents to ensure accuracy. Extreme outcome values and range checks were performed for age at assessment across all outcomes, including fetal brain assessment, Bayley-III scores, BERA results, and indicators of eye-tracking assessment. All data reviews and cleaning procedures were performed while the investigators were blinded to treatment allocation.

#### **3.4. Definition of Baseline**

Baseline assessments were performed between 18–22 weeks of gestation to collect data on potential covariates, including sociodemographic characteristics, anthropometric measurements, and hemoglobin assessment.

#### **3.5. Definition of analysis populations**

For all outcomes, we will perform complete-case analysis, which include all subjects with outcome data regardless their compliance to the intervention.

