### **3.9. Handling of Missing Data**

We will handle missing data first by tabulating the proportion of subjects lost to follow-up by allocation groups and examining if missingness differs significantly (e.g., >10% absolute difference) by allocation groups or key baseline characteristics. Additionally, baseline characteristics of participants with available outcome data will be compared to those with missing outcome data. To further assess potential bias introduced by missingness, we will evaluate balance in baseline covariates between allocation groups, both in the original trial sample and the sample retained at follow-up. Efficacy analyses and other exploratory analyses will be performed in the full analysis set (i.e., all subjects randomly assigned to the study, including those who did not receive a dose of study treatment).

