### 4.2. Baseline Characteristics

We will present characteristics of the study sample with continuous data as mean and SD or as median with 25th and 75th percentiles. Categorical variables will be presented as frequencies and percentages. We will indicate sample sizes for variables with more than 20% missing observations in the footnotes. Variables of the baseline characteristics are listed in **Table 1**, which best describe the study population, particularly in relation to child nutrition and cognition, as our predictor and outcome of interest in this analysis.

**Table 1.** Characteristics of the study sample

Variable	Definition
Baseline	
Child sex	2 categories: Female or male
Birth order	2 categories: First born or $\geq$ second-born
Municipality economic status	2 categories: High (Central and South Jakarta) or low (North and East Jakarta)
Maternal height	Maternal height in centimeters
Maternal pre-pregnancy BMI	BMI in kg/m 
Maternal hemoglobin level at baseline	Hemoglobin level in g/L
Maternal history of hypertension	2 categories: With a history of hypertension or without any history of hypertension
Maternal age	Maternal age in years
Maternal education	3 categories: No education/incomplete primary/unknown, Completed primary, Completed secondary or greater
Number of children	Number of children under 5 years old in the household
Number of household members	Total number of people in the household
Maternal marital status	3 categories: Monogamous marriage, polygamous marriage, or unmarried [single, divorced, widowed]
Maternal occupation	2 categories: Housewife or working mother
Paternal occupation	2 categories: Non-private sector and unemployed, or private sector
Monthly household expenditure	Household expenditure in Indonesian Rupiah per month
Endline	
Child age at outcome assessment	Child age in months (or gestational week for fetal brain outcome)
HOME inventory	HOME inventory score at the age of 4–6 months

Screen time	Screen time per day in minutes at the age of 4–6 months
-------------	---

HOME inventory, the Home Observation for Measurement of the Environment inventory.

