## 5. ANALYSIS OF THE PRIMARY OUTCOME(S)

### 5.1. Main Analysis

We will perform all analyses after the last participant in the follow-up study has completed their visit. We will review the characteristics of the study sample as blinded cohort. First, we will use fake IDs and scrambled group code to write the script for analysis and create dummy tables and figures. Once the script, tables, and figures are ready, we will insert the correct IDs with blinded group code (e.g., A vs. B) and create the draft of the interpretation of the results for each case (e.g., if “A” is the Control group vs. if “A” is the Intervention group). We will finally reveal the group assignments after all authors have reviewed and approved the results for the primary outcomes. Unblinded analyses will be performed for secondary analyses, such as effect modification and subgroup analyses.

For all outcomes, the primary analysis to answer each objective will be a minimally adjusted model controlling only for child age at assessment and the randomization stratification factors (maternal education and municipality economic status). In secondary analyses, we will estimate adjusted parameters by including additional covariates—baseline characteristics, as well as post-enrollment and follow-up variables—in addition to those included in the primary analyses.

Unless otherwise specified, we will use two-sided confidence intervals at the 0.05 significance level for all analyses. For example, we are not powered to conduct subgroup/effect-modification analyses, so these secondary objectives will be exploratory and considered significant at the  $\alpha=0.10$  level. All hypothesis testing in this analysis plan is based on a two-sided superiority framework.

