#### 5.1.2 Baseline and fully adjusted analyses

We will also perform baseline and fully adjusted analyses with covariates for each outcome. First, we will perform bivariate analyses using the likelihood ratio test to test the association between the covariates with each outcome. Covariates with a p-value < 0.1 will be included in the adjusted analysis. Covariates with little variation in the study population (e.g., prevalence < 5%) will be

excluded. We will also evaluate the collinearity between potential covariates using the Variance Inflation Factor.

Potential covariates are listed below:

- Child sex: female or male
- Birth order: first-born or  $\geq$  second-born
- Municipality economic status: High or low
- Maternal height in centimeters
- Maternal pre-pregnancy BMI: BMI in  $\text{kg}/\text{m}^2$
- Maternal hemoglobin level at baseline in  $\text{g}/\text{L}$
- Maternal history of hypertension at baseline: With or without any history of hypertension
- Maternal age in years
- Maternal education: no education/incomplete primary/unknown, completed primary (6 years of formal education), completed secondary (9 years of formal education), completed greater than secondary
- Number of children under 5 yo in the household
- Number of household members
- Maternal marital status: monogamous marriage, polygamous marriage, or unmarried [single, divorced, widowed]
- Maternal occupation: housewife or working mother
- Paternal occupation: non-private sector and unemployed or private sector
- Monthly household expenditure in Indonesian Rupiah per month
- HOME inventory score (home environment)
- Screen time per day in minutes
- Staff members performing the assessment (for Bayley-III)

Two versions of adjusted analyses will be conducted as described below.

- Baseline adjusted model: This model will include covariates in minimally adjusted model and any of the following baseline covariates that are significantly associated at  $p < 0.1$  with the outcomes: child sex, birth order, maternal height, maternal pre-pregnancy BMI, maternal hemoglobin, maternal age, paternal age, paternal education, number of children under 5 yo in the household, number of household members, maternal marital status, maternal occupation, paternal occupation, household expenditure.

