- Fully adjusted model: Then, we will adjust for any covariates collected at follow-up (HOME inventory score, screen time) that are significantly associated at  $p < 0.1$  with the outcomes. For any covariates collected after baseline, we will check whether any differences are based on allocation groups at  $p < 0.1$ . Significant differences indicate potential mediators. Therefore, we will exclude them from the model.

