## 5.2. Sensitivity Analyses

In all primary analyses for the primary outcomes, inverse probability of censoring weights (IPCW) will be estimated to address potential bias from outcome attrition. The missingness model will be fit using logistic regression with a prespecified set of covariates, including allocation group, randomization stratification factors (maternal education and municipality economic status), baseline characteristics listed in **Table 1**, and other primary outcomes measured prior to the outcome visit (e.g., fetal whole brain volume when modeling the cognitive score) that are plausible predictors of both censoring and the outcome. Stabilized weights will be computed conditional on allocation group and the randomization stratification factors, and weights will be truncated at the 1st and 99th percentiles (0.5th and 99.5th in sensitivity analyses). Diagnostics will include summaries of the weight distribution, effective sample size, and covariate balance before and after weighting. Robustness to model misspecification will be assessed using augmented IPCW estimators.

We will not perform a per-protocol analysis given the high compliance with both the probiotics/placebo and omega-3 FAs interventions.

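### The analysis population is defined by outcome data alone, with no rule for missing covariates, so the adjusted and IPCW analyses can rest on smaller, different samples than the primary estimate

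*SAP*

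**What the plan says.** SAP 3.5 sets one population for all outcomes: "For all outcomes, we will perform complete-case analysis, which include all subjects with outcome data regardless their compliance to the intervention". SAP 3.9 places efficacy analyses in a full analysis set described as "all subjects randomly assigned to the study, including those who did not receive a dose of study treatment". Its handling of missing data consists of tabulations and balance checks on loss to follow-up and missing outcomes. It does not mention missing covariates.

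The models differ in what they need:

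- **Primary (5.1, 5.1.1):** "a minimally adjusted model controlling only for child age at assessment and the randomization stratification factors".
- **Baseline adjusted (5.1.2):** the primary terms plus any of 14 listed baseline covariates that pass a bivariate screen for that outcome. "Covariates with a p-value < 0.1 will be included in the adjusted analysis".
- **Fully adjusted (5.1.2):** also HOME score and screen time, collected at 4–6 months, if associated with the outcome and not different between arms at p < 0.1.
- **IPCW (5.2):** a missingness model with allocation, the stratification factors, Table 1 baseline characteristics and "other primary outcomes measured prior to the outcome visit (e.g., fetal whole brain volume when modeling the cognitive score". An augmented version is to follow.

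The SAP allows for gaps in these variables. Section 4.2 has a reporting convention, "We will indicate sample sizes for variables with more than 20% missing observations in the footnotes", and section 2.8 records that during the pandemic "mothers might not attend MRI assessment and blood sample collection if not comfortable". The only analysis provision for a missing covariate is the unknown level within maternal education.

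**The concern.** A population defined by the outcome is enough only when every other term in the model is observed. That is essentially so for the primary model. The other models need variables that may be absent for some subjects who have the outcome. With complete-case as the only stated principle, and with the usual default of regression software, those subjects leave the model.

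The primary, baseline adjusted, fully adjusted and weighted estimates will be read side by side. If their samples differ, a shift may come from covariate adjustment, from correction for attrition, or simply from the change of subjects, and the reader cannot tell which. Each p < 0.1 screen may also run on its own subset.

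The IPCW analysis matters most, because addressing attrition is its stated purpose. A subject with an observed outcome but a missing predictor gets no weight, so the analysis would add a second layer of loss to the one it is meant to address.

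**Working it through.** **Inputs.** Randomised: 157 per arm, 314 in total (SAP 2.4). Anticipated attrition 33.3%, effect 0.40 SD, α = 0.05, power 0.80 (SAP 2.6). Two-sided testing (SAP 5.1). The SAP gives no covariate missingness rate, so every rate below is assumed.

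**Plan's own figure.** n per arm = 2(1.96 + 0.8416)² / 0.40² = 98.1, rounded up to 99, so 198 in total. Allowing for attrition, 198 / (1 − 0.333) = 297. The stated minimum of 300 reproduces.

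**Expected with an outcome.** 314 × 2/3 = 209.3, about 209.

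**Effect of dropping rows.** Let q be the share of those 209 with at least one needed covariate missing. Then n = 209.3(1 − q), and power = Φ(0.40·√(n/4) − 1.96), unadjusted. If dropping is unrelated to anything else, the smaller sample is a random subset. The difference between its estimate and the full-sample estimate then has standard deviation √(4/n − 4/209.3) in SD units.

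| q (assumed) | n | Power for 0.40 SD | Chance shift between the two estimates (SD units) |
|---|---|---|---|
| 0 | 209 | 82.5% | 0 |
| 5% | 199 | 80.5% | 0.03 |
| 10% | 188 | 78.4% | 0.05 |
| 20% | 167 | 73.5% | 0.07 |
| 33.3% | 140 | 65.6% | 0.10 |

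Example of the last column at 20%: √(4/167.5 − 4/209.3) = √(0.02388 − 0.01911) = 0.07. This is the typical shift when the dropped subjects are no different from the rest. If they do differ, a systematic shift is added.

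**Small gaps accumulate.** If all 14 baseline covariates entered, each independently missing in 1%, 2% or 3% of subjects, the complete share would be 0.99¹⁴ = 86.9%, 0.98¹⁴ = 75.4% or 0.97¹⁴ = 65.3%, that is 182, 158 or 137 of 209. Gaps that cluster in the same women would cost less.

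**Two cases built into the plan.**

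1. *IPCW for the cognitive score.* Section 5.2 names fetal whole brain volume as a predictor in the missingness model, and section 2.8 says the MRI could be missed. A child with a Bayley-III score but no MRI has no fitted probability and so no weight. In one simulated set of 314 (outcome missing for 33.3% and MRI volume independently missing for 33.3%, both assumed), 208 had an outcome and 130 of them received a weight.
2. *Fetal outcomes in the fully adjusted model.* Brain volume is measured at 36–38 weeks, but HOME score and screen time at 4–6 months. If either passes the screens for a fetal outcome, everyone who left after the MRI drops from that model.

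**The case against.** The strongest reply is that this is an omission. Section 3.5 does not say that every model keeps every subject with an outcome, and nowhere does the SAP say that rows with a missing covariate are deleted. That is inferred from the term complete-case and from software defaults. This stands, and a reader who infers a flat contradiction within the SAP goes too far. But complete-case is the only rule given, and an analyst who follows it would drop these subjects.

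Several other limits stand:

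- The 20% in section 4.2 is a footnote threshold for a descriptive table that also holds endline variables. A reader might infer that the plan expects a fifth of subjects to be lost from the adjusted models. It does not say so, and 20% is used above only as one assumed value.
- The power figures are unadjusted. Covariates that predict the outcome would recover some precision, and the power target in section 2.6 was not set for these secondary models. The figures only index lost information.
- Section 5.1 presents the adjusted models as secondary analyses and gives them no checking role. Only the IPCW analysis has one.
- The predictors in section 5.2 can be read as limited to plausible predictors of both censoring and outcome, so not every Table 1 item need enter. That section also requires effective sample size and balance diagnostics, which would help to reveal shrinkage. They would not prevent it.
- Baseline data come from one assessment window (section 3.4), so gaps may cluster.

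**Conclusion.** The point holds for the baseline adjusted, fully adjusted and IPCW analyses. They need variables that section 3.5 ignores, section 3.9 does not cover and other sections allow to be missing. As written, their samples can be smaller than the primary one and differ from it.

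A reader might infer that the primary result is compromised. The documents do not support that: the minimally adjusted model needs only age at assessment and the two stratification factors, and is unaffected.

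The size is unknown. Assumed losses of 5% to 33.3% take about 209 subjects to between 199 and 140, and unadjusted power from 82.5% to between 80.5% and 65.6%. Chance alone could then move an estimate by about 0.03 to 0.10 SD, against a design effect of 0.40 SD. With fully observed covariates there would be no loss. Because covariates enter only through the p < 0.1 screens, the loss will also vary by outcome. The two built-in cases need no assumption about careless data collection, only that some mothers missed the MRI or left after it and that the variable concerned enters the model.

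**What to change.** In 3.5, 5.1.2 and 5.2:

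1. State that a missing baseline covariate is filled with the pooled, arm-blind mean or mode plus a missing indicator, in the p < 0.1 screens, the adjusted models and the IPCW and augmented IPCW models.
2. In the IPCW models, treat an unobserved earlier outcome, such as MRI volume, in the same way, with an indicator that it was not measured. Filling baseline items alone would still leave children without an MRI unweighted.
3. Where HOME score or screen time still reduces the sample, refit the minimally and baseline adjusted models on the same subjects and show them beside the fully adjusted model.
4. Report N for every model.

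The cost is a few sentences of SAP text, a little more code and slightly weaker covariate adjustment than with fully observed covariates. Simple imputation is justified for baseline covariates in a randomised comparison. It does not by itself remove bias from outcome attrition, and the SAP should not claim that it does.
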